# Management of Hyperphosphatemia

Hyperphosphatemia is a recognized on-target effect of potent and selective inhibitors of the FGFR pathway. While on BGJ398, patients should avoid foods that are especially high in phosphate and, if possible, should restrict dietary phosphate to 600 – 800 mg/day. High-phosphate foods include dairy products; meats, nuts, and other high-protein foods; processed foods; and dark colas.

Patients who have experienced hyperphosphatemia should take a phosphate binder such as sevelamer, sucroferric oxyhydroxide, lanthanum carbonate, ferric citrate, etc. within 30 minutes of a meal on the day while taking BGJ398. Once the patient has had hyperphosphatemia, the patient should remain on a low phosphate diet, if possible, and take phosphate binder on the days BGJ398 is taken, even if the serum phosphorus is normalized. Unless otherwise specified by the local package insert or institutional practice, the following regimen should be used to manage hyperphosphatemia:

- For serum phosphorus > 5.5 7.5 mg/dL
  - Start sevelamer 800 mg three times a day with meals
  - Increase the dose of sevelamer up to 1200 mg every 8 hours
- For serum phosphorus ≥7.5 mg/dL
  - o Increase the dose of sevelamer up to 1600 mg (2 tablets per meal) every 8 hours
  - Consider adding acetazolamide two to three 250 mg tablets per day.

During the BGJ398 cycle, patients do not need to be on a low phosphate diet or take a phosphate binder during their 1-week off period unless serum phosphorus is not normalized. Other dose modifications are provided in Table 5, but should be modified as per country or institutional practice.

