The overall observation period will be divided into three mutually exclusive segments:

pre-treatment period: from day of subject's first informed consent to the day before first administration of study treatment

on-treatment period: from date of first administration of study treatment to 30 days after date of last actual administration of any study treatment (including start and stop date).

post-treatment period: starting at Day 31 after last administration of study treatment in the single arm.

If dates are incomplete in a way that clear assignment to pre-, on-, post-treatment period cannot be made, then the respective data will be assigned to the on-treatment period.

Safety summaries (tables, figures) include only data from the on-treatment period with the exception of baseline data which will also be summarized where appropriate (eg, change from baseline summaries). In addition, a separate summary for death including on-treatment and post treatment deaths will be provided. Summary tables for adverse events (AEs) will summarize only on-treatment events, with a start date during the on-treatment period (***treatment-emergent AEs***).

2.1.1.6 *Handling of Missing Values/Censoring*

Subjects who are of unknown clinical response or not assessed will be treated as nonresponders in the analyses of overall response rate (ORR).

Subjects who haven't experienced the specified event at the time of analysis will have time-to-event data (eg, progression-free survival, overall survival, etc.) censored at the time of last measurement prior to the data cut-off point used in the report.

2.2 *Analysis Sets*

2.2.1 *Full Analysis Set*

The Full Analysis Set (FAS) includes all subjects who received at least one dose of infigratinib. Unless otherwise specified, all the analyses will be done separately for each cohort.

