- All TEAEs occurred in $\geq 10\%$ subjects by PT by descending order of frequency
- Grade 3 or 4 TEAEs by PT by descending order of frequency
- Treatment related Grade 3 or 4 TEAEs by PT by descending order of frequency
- Treatment emergent serious AEs (SAEs) by PT by descending order of frequency
- Treatment emergent serious treatment-related AEs by PT by descending order of frequency
- TEAE leading to treatment discontinuation by PT by descending order of frequency
- TEAE requiring additional medication or therapies by descending order of frequency

The following listings will be produced:

- All adverse events
- All serious adverse events

Deaths

Primary reason for on-treatment, post-treatment and all deaths will be summarized for the full analysis set. Treatment-emergent AE with fatal outcome will be summarized by SOC and PT. On-treatment death will also be summarized by SOC and PT.

All deaths will be listed and on-treatment death will be flagged.

Adverse Events of Special Interest

Adverse events of special interest (AESI) will be considered. Each AESI consists of one or more well-defined safety events which are similar in nature and for which there is a specific clinical interest in connection with the study treatment(s) (Section 5.2 to Section 5.8). For each specified AESI, number and percentage of patients with at least one event within the AESI will be reported. The following AESI will be considered for this study:

- Calcium phosphate homeostasis, including the subcategories of hypercalcemia, hyperphosphatemia, and hypophosphatemia
- Eye disorder
- Central Serious Retinopathy/Retinal Pigment Epithelium Detachment (CSR/RPED)
- Cardiac disorder
- Acute pancreatitis
- Tissue calcification
- Pathological fracture
- Vascular calcification/mineralization

For each AESI (or its subcategory), the overall summary of the characteristics will be provided. In addition, each AESI will also be summarized by subcategory (as applicable), preferred term and worst grade. The current search strategy for each AESI is documented in Section 5.2.

Minimum Critical Toxicities

Minimal critical toxicities are toxicities that should always be explicitly considered during the planning for the development of every new medicinal product (Section 5.9). Analyses of these are based on FDA guidance as applicable (ie, Drug Induced Liver Injury using Hy's Law per FDA guidance).

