| Adverse Event of Special Interest | Search Strategy |
|--|--|
| Calcium-phosphate homeostasis ¹ 
• Hypercalcaemia• Hyperphosphataemia• Hypophosphataemia | Sponsor-defined grouped PTs |
| Eye disorder ² | Sponsored-defined PTs in SOC Eye disorder: CSR/RPED Eye disorder other than RPED |
| Central serous retinopathy/retinal pigment epithelium detachment (CSR/RPED) ³ | Subset of PTs from SOC Eye disorders |
| Cardiac disorder* | Cardiac failure SMQ [narrow, broad] Myocardial infarction SMQ [narrow, broad] Other ischaemic heart disease SMQ [narrow, broad] Cardiac arrhythmia terms, nonspecific SMQ [narrow] Bradyarrhythmia terms, nonspecific SMQ [narrow] Tachyarrhythmia terms, nonspecific SMQ [narrow] Arrhythmia related investigations, signs and symptoms SMQ [narrow, broad] |
| Acute pancreatitis | Acute pancreatitis SMQ [narrow, broad] |
| Pathological fracture ⁴ | Sponsor-defined PTs |
| Tissue calcification ⁵ | Sponsor-defined PTs |
| Vascular/intravascular mineralization ⁶ | Sponsor-defined Grouped PTs |

* Note: SMQs relating to Torsade de Pointes / QT prolongation and cardiac arrhythmias are part of Minimum Critical Toxicity: Cardiac toxicity Rationales for Sponsor-defined grouped terms:

¹ Sponsor-defined PTs capture the medical concept of hypercalcaemia, hyperphosphataemia, and hypophosphataemia. No SMQs available for these terms.

² Sponsor-defined PTs in the SOC Eye Disorders, including 9 PTs used to characterize CSR/RPED, broadly capture eye related events. No SMQ available for this medical concept.

³ A narrow subset of PTs from SOC Eye Disorder (as selected by an ophthalmologist) are grouped to capture the medical concept of RPED. No SMQ available for this medical concept.

⁴ Sponsor-defined PTs include PTs with 'fracture', which capture the broad medical concept of fractures, recognizing that any fracture could be pathological in nature for the population under study. No SMQ available for this medical concept.

⁵ Sponsor-defined PTs include PTs with 'calcification' and 'calcinosis' which capture the broad medical concept of tissue calcification. No SMQ available for this medical concept.

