⁶ Sponsor-defined PTs include PTs with targeted root words (athero, arterio, and sclerosis) and words (arterial, artery, calcification, insufficiency, mineralization, peripheral, and venous) with medical judgement to refine on terms which capture the broad medical concept of vascular calcification/mineralization. No SMQ available for this medical concept.

5.3 AESI: Calcium-Phosphate Homeostasis – Hypercalcaemia, Hyperphosphataemia, and Hypophosphataemia

| AESI | Sponsor-Defined Grouped PTs |
|--------------------|---|
| Hypercalcaemia | Adjusted calcium increased Blood calcium abnormal Blood calcium increased Calcium ionised abnormal Calcium ionised increased Calcium phosphate product increased Hypercalcaemia |
| Hyperphosphataemia | Blood phosphorus abnormal Blood phosphorus increased Hyperphosphataemia |
| Hypophosphataemia | Blood phosphorus decreased Hypophosphataemia |

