5.6 AESI: Tissue Calcification

| Sponsor-Defined Grouped PTs | Sponsor-Defined Grouped PTs | Sponsor-Defined Grouped PTs |
|-----------------------------------|---|---------------------------------|
| Administration site calcification | Infusion site calcification | Splenic calcification |
| Adrenal calcification | Injection site calcification | Tendon calcification |
| Application site calcification | Intervertebral disc calcification | Thyroid calcification |
| Articular calcification | Intestinal calcification | Tracheal calcification |
| Bladder wall calcification | Ligament calcification | Vaccination site calcification |
| Bone decalcification | Lymph node calcification | Calcinosis |
| Breast calcifications | Medical device site calcification | Chondrocalcinosis |
| Bursa calcification | Myocardial calcification | Chondrocalcinosis pyrophosphate |
| Calcification metastatic | Ovarian calcification | Gastric mucosal calcinosis |
| Calcification of muscle | Pancreatic calcification | Nephrocalcinosis |
| Catheter site calcification | Pericardial calcification | |
| Cerebral calcification | Pleural calcification | |
| Cutaneous calcification | Postoperative heterotopic calcification | |
| Dystrophic calcification | Primary familial brain calcification | |
| Hepatic calcification | Prostatic calcification | |
| Implant site calcification | Pulmonary calcification | |

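### SAP 5.6 counts the preferred term Bone decalcification as tissue calcification, although the term means the reverse

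*SAP*

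**What the plan says.** SAP 5.2 gives a search strategy for each AESI, with a footnote explaining each sponsor-defined list. Footnote 5 describes the tissue-calcification list as the terms containing 'calcification' or 'calcinosis', "which capture the broad medical concept of tissue calcification". SAP 5.6 then sets out the list, which includes "Bone decalcification".

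SAP 2.7.2.1.2 governs the reporting. For each AESI, the "number and percentage of patients with at least one event within the AESI will be reported". Below that level, "each AESI will also be summarized by subcategory (as applicable), preferred term and worst grade". SAP 2.2.1 adds the level at which this is done: "Unless otherwise specified, all the analyses will be done separately for each cohort".

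On the related term, SAP 5.3 puts the calcium-phosphate product in the hypercalcaemia group only: "Calcium ionised increased Calcium phosphate product increased Hypercalcaemia". Footnote 1 in SAP 5.2 covers the three calcium-phosphate subcategories together: "Sponsor-defined PTs capture the medical concept of hypercalcaemia, hyperphosphataemia, and hypophosphataemia".

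**The concern.** Tissue calcification is a specific safety question for this drug. Protocol 1.2.1.1.2 reports ectopic mineralization in animals as an on-target effect, and exclusion criterion 6 keeps out patients with extensive tissue calcification. The AESI row should therefore contain events that point towards calcification.

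Bone decalcification points the other way. Because one listed event is enough, a patient with only that term enters the numerator as a case. The error has one direction: the extra term can add patients to the row and cannot remove any. At stake is whether one descriptive safety percentage can be trusted. No efficacy result and no trial decision depends on it.

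**Working it through.** The SAP states no figure to reproduce. The check sets the lists, footnotes and counting rule side by side.

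**1. The list.** SAP 5.6 has three columns of 16, 16 and 10 terms: 16 + 16 + 10 = 42. Bone decalcification is 1 of the 42.

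**2. Term against concept.** The stated concept is mineral deposited in tissue. The plain meaning of the term is mineral lost from bone. The only link to footnote 5 is that the string 'calcification' occurs inside 'decalcification'. Neither document gives a clinical reason for including it.

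**3. Comparison with the neighbouring lists.**
- Footnote 4 (fractures) explains its breadth: in this population any fracture might be pathological.
- Footnote 6 (vascular mineralization) says the word search was refined by medical judgement.
- Footnote 5 says neither.
- SAP 5.6 is not an untouched word search, however. Six terms containing the word appear in SAP 5.7 and not in 5.6: vascular calcification, heart valve calcification, and aortic, mitral, pulmonary and tricuspid valve calcification. Terms have been allocated between the two lists, so removing one more is consistent with how they were built.

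**4. Effect of the counting rule.** If k patients in a group of N have Bone decalcification as their only listed term, the reported percentage rises by 100 × k / N points. The documents give no value for k, so k = 0, 1 or 3 is an assumption. N is the planned size.

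| Group | N | k = 0 | k = 1 | k = 3 |
|---|---|---|---|---|
| Cohort 1 | 120 | 0 | 100/120 = 0.8 | 300/120 = 2.5 |
| Cohort 1, FGFR2 fusion or translocation | 106 | 0 | 100/106 = 0.9 | 300/106 = 2.8 |
| Cohort 2, or Cohort 3 if expanded | 20 | 0 | 100/20 = 5 | 300/20 = 15 |

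The last cell is arithmetic only. Three such patients in 20 would be six times the rate of three in 120, and nothing in the documents suggests that.

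**5. The calcium-phosphate product.** A product can rise through either factor.
- *Through phosphate.* Protocol 6.3.1 says: "Hyperphosphatemia is a recognized on-target effect of potent and selective inhibitors of the FGFR pathway". Exclusion criterion 14 uses a product threshold of 55 mg²/dL², listed separately from calcium and from phosphorus. It is an eligibility limit and is used here only for scale. At phosphorus 7.5 mg/dL, the top of the band in Protocol Table 5 where the dose is maintained, the product reaches 55 at calcium 55 / 7.5 = 7.3 mg/dL. Taking normal calcium as about 8.5 to 10.5 mg/dL (assumed, not in the documents), that is below normal.
- *Through calcium.* At an assumed phosphorus of 4.5 mg/dL, the product reaches 55 at calcium 55 / 4.5 = 12.2 mg/dL, which is high calcium on the same assumed range.

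The term is therefore mixed. The hypercalcaemia row may or may not be right for a given patient, whereas Bone decalcification does not fit its list at all.

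**The case against.** The best defence is that the list follows a disclosed rule and is broad on purpose. The fracture list is built in the same way and takes in fracture of penis and tooth fracture. The AESIs were aligned with a program-wide definition in SAP version 2.0, so a change in this study alone would break consistency. The preferred-term rows name the term, so a reader can subtract it.

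Parts of this stand. Breadth is a legitimate choice, consistency has value, and the by-term display limits any harm. But breadth justifies doubtful members, not one of opposite meaning; the odd fracture terms still contain fractures. Program-wide use is also a reason to correct the source definition.

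A reader might infer that the calcium-phosphate product is a second misclassification of the same kind. The documents do not support that:
- The product can be calcium-driven, in which case the row is correct.
- Footnote 1 covers the three calcium-phosphate concepts jointly and does not say where a mixed term belongs.
- The parent AESI count is the same wherever the term sits.
- The same list holds two terms without direction (blood calcium abnormal, calcium ionised abnormal), which can be defended as deliberate sensitivity. That reasoning also covers the product.
- Protocol Table 9 has no product test. Protocol 8.1.2 prefers a diagnosis and does not require a result to be recorded again when it corresponds to an event already reported. A patient with only the product term may therefore be rare.
- Corrected calcium is graded from laboratory values and tabulated by direction (SAP 2.7.2.2), so hypercalcaemia can be checked independently.

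**Conclusion.** The Bone decalcification entry is a genuine but minor list error. It rests on the plain meaning of the term and on the at-least-one-event rule; neither document justifies the entry. The overstatement is 100/N points per affected patient: 0.8 in Cohort 1 and 5 in a cohort of 20. The number affected is unknown and may be zero.

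It would go too far to infer that the tissue-calcification rate will be inflated or that a safety conclusion is biased. The documents give no sign that the event occurs, the by-term rows expose it, and no dosing, interim or efficacy rule uses the percentage. The placement of the calcium-phosphate product is a grouping choice that would benefit from a note.

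**What to change.** Delete Bone decalcification from SAP 5.6 before database lock. Make the same edit in the program-wide AESI definition, or footnote the difference. The cost is one list edit and, if the program list is left alone, a small departure from it. No event disappears from reporting, because the term stays in the tables by system organ class and preferred term.

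Optionally, add a footnote to SAP 5.3 saying that a raised calcium-phosphate product can be phosphate-driven, or show the term on its own line under the parent AESI. The second choice has a cost: it takes calcium-driven events out of the hypercalcaemia row, which could then be understated. The footnote avoids that.

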5.4 AESI: Eye Disorder of Central Serous Retinopathy/Retinal Pigment Epithelium Detachment

AESI of Eye disorder is characterized by PTs from SOC Eye disorders. CSR/RPED terms are listed below and remaining eye disorders (excluding PTs used to characterize CSR/RPED) are listed in Section 5.8.

| AESI | Sponsor-Defined Grouped PTs |
|---|--|
| Central serous retinopathy/retinal pigment epithelium detachment (CSR/RPED) | Chorioretinopathy Detachment of macular retinal pigment epithelium Detachment of retinal pigment epithelium Macular detachment Retinal detachment Serous retinal detachment Subretinal fluid MEK inhibitor-associated serous retinopathy Retinopathy |

5.5 AESI: Pathological Fracture

| Sponsor-Defined Grouped PTs | Sponsor-Defined Grouped PTs | Sponsor-Defined Grouped PTs |
|-------------------------------|---|------------------------------------|
| Fracture | Fracture nonunion | Osteochondral fracture |
| Acetabulum fracture | Fracture of clavicle due to birth trauma | Osteophyte fracture |
| Ankle fracture | Fracture of penis | Osteoporotic fracture |
| Atypical femur fracture | Fracture pain | Patella fracture |
| Atypical fracture | Fracture reduction | Pathological fracture |
| Avulsion fracture | Fracture treatment | Pelvic fracture |
| Cervical vertebral fracture | Fractured coccyx | Periprosthetic fracture |
| Chance fracture | Fractured ischium | Pseudofracture |
| Clavicle fracture | Fractured maxilla elevation | Pubis fracture |
| Closed fracture manipulation | Fractured sacrum | Radius fracture |
| Comminuted fracture | Fractured skull depressed | Rib fracture |
| Complicated fracture | Fractured zygomatic arch elevation | Sacroiliac fracture |
| Compression fracture | Greenstick fracture | Scapula fracture |
| Costal cartilage fracture | Hand fracture | Skull fracture |
| Craniofacial fracture | Hip fracture | Skull fractured base |
| Elevation skull fracture | Humerus fracture | Spinal compression fracture |
| Epiphyseal fracture | Ilium fracture | Spinal fracture |
| External fixation of fracture | Impacted fracture | Spinal fusion fracture |
| Facial bones fracture | Internal fixation of fracture | Sternal fracture |
| Femoral neck fracture | Jaw fracture | Stress fracture |
| Femur fracture | Limb fracture | Subchondral insufficiency fracture |
| Fibula fracture | Lisfranc fracture | Surgical fixation of rib fracture |
| Foot fracture | Loss of anatomical alignment after fracture reduction | Thoracic vertebral fracture |
| Forearm fracture | Lower limb fracture | Tibia fracture |
| Fracture blisters | Lumbar vertebral fracture | Tooth fracture |
| Fracture debridement | Metaphyseal corner fracture | Torus fracture |
| Fracture delayed union | Multiple fractures | Traumatic fracture |
| Fracture displacement | Open fracture | Ulna fracture |
| Fracture infection | Open reduction of fracture | Upper limb fracture |
| Fracture malunion | Open reduction of spinal fracture | Wrist fracture |

5.6 AESI: Tissue Calcification

| Sponsor-Defined Grouped PTs | Sponsor-Defined Grouped PTs | Sponsor-Defined Grouped PTs |
|-----------------------------------|---|---------------------------------|
| Administration site calcification | Infusion site calcification | Splenic calcification |
| Adrenal calcification | Injection site calcification | Tendon calcification |
| Application site calcification | Intervertebral disc calcification | Thyroid calcification |
| Articular calcification | Intestinal calcification | Tracheal calcification |
| Bladder wall calcification | Ligament calcification | Vaccination site calcification |
| Bone decalcification | Lymph node calcification | Calcinosis |
| Breast calcifications | Medical device site calcification | Chondrocalcinosis |
| Bursa calcification | Myocardial calcification | Chondrocalcinosis pyrophosphate |
| Calcification metastatic | Ovarian calcification | Gastric mucosal calcinosis |
| Calcification of muscle | Pancreatic calcification | Nephrocalcinosis |
| Catheter site calcification | Pericardial calcification | |
| Cerebral calcification | Pleural calcification | |
| Cutaneous calcification | Postoperative heterotopic calcification | |
| Dystrophic calcification | Primary familial brain calcification | |
| Hepatic calcification | Prostatic calcification | |
| Implant site calcification | Pulmonary calcification | |

5.7 AESI: Vascular/intravascular Mineralization

| Sponsor-Defined Grouped PTs | Sponsor-Defined Grouped PTs | Sponsor-Defined Grouped PTs |
|---|--|--|
| Acute vascular insufficiency of intestine | Coeliac artery occlusion | Peripheral artery restenosis |
| Aortic arteriosclerosis | Coeliac artery stenosis | Peripheral artery stenosis |
| Aortic valve calcification | Coronary artery disease | Peripheral vascular disorder |
| Arterial insufficiency | Coronary artery insufficiency | Precerebral arteriosclerosis |
| Arterial insufficiency coronary | Coronary artery occlusion | Precerebral artery occlusion |
| Arterial insufficiency peripheral | Coronary artery reocclusion | Pulmonary artery occlusion |
| Arteriosclerosis | Coronary artery restenosis | Pulmonary artery stenosis |
| Arteriosclerosis coronary artery | Coronary artery stenosis | Pulmonary valve calcification |
| Arteriosclerotic retinopathy | Heart valve calcification | Renal arteriosclerosis |
| Atherosclerotic plaque rupture | Hepatic artery flow decreased | Renal artery arteriosclerosis |
| Basilar artery occlusion | Hepatic artery occlusion | Renal artery occlusion |
| Basilar artery stenosis | Hepatic artery stenosis | Renal artery restenosis |
| Basilar insufficiency | Iliac artery disease | Renal artery stenosis |
| Brachiocephalic arteriosclerosis | Iliac artery occlusion | Retinal artery occlusion |
| Brachiocephalic artery occlusion | Inner ear vascular insufficiency | Retinal artery stenosis |
| Brachiocephalic artery stenosis | Insufficiency cerebrovascular | Splenic artery stenosis |
| Carotid arteriosclerosis | Insufficiency coronary artery | Subclavian artery occlusion |
| Carotid artery insufficiency | Intraoperative cerebral artery occlusion | Subclavian artery stenosis |
| Carotid artery occlusion | Mesenteric arteriosclerosis | Tricuspid valve calcification |
| Carotid artery restenosis | Mesenteric artery stenosis | Unspecified vascular insufficiency of intestine |
| Carotid artery stenosis | Mesenteric vascular insufficiency | Vascular calcification |
| Cerebellar artery occlusion | Microvascular coronary artery disease | Vascular insufficiency |
| Cerebral arteriosclerosis | Mitral valve calcification | Vascular insufficiency of intestine |
| Cerebral artery occlusion | Penile artery occlusion | Vascular insufficiency of intestine, unspecified |
| Cerebral artery restenosis | Peripheral arterial occlusive disease | Vertebral artery occlusion |
| Cerebral artery stenosis | Peripheral arterial reocclusion | Vertebral artery stenosis |
| Cerebrovascular insufficiency | Peripheral artery occlusion | Vertebrobasilar insufficiency |
| Chronic vascular insufficiency of intestine | | |

5.8 AESI: Eye Disorder: SOC Eye Disorders (Excluding 9 PTs Used to Characterize CSR/RPED)

There are two subcategories in the eye disorder AESI summary table, one for CSR/RPED which included 9 PTs described in Section 5.4, the other is Eye Disorder SOC Other than CSR/RPED which included the remaining eye disorders not included in CSR/RPED section and are described in this section.

| SOC Eye Disorders | SOC Eye Disorders | SOC Eye Disorders |
|--------------------------------------|---|--------------------------------|
| Abnormal sensation in eye | Exfoliation syndrome | Ocular ischaemic syndrome |
| Abscess of eyelid | Exophthalmos | Ocular lymphoma |
| Acanthamoeba keratitis | Exophthalmos congenital | Ocular myasthenia |
| Accommodation disorder | Exposure keratitis | Ocular neoplasm |
| Acquired corneal dystrophy | Extraocular muscle disorder | Ocular pemphigoid |
| Acquired epiblepharon | Extraocular muscle paresis | Ocular procedural complication |
| Acquired lenticonus | Extraocular retinoblastoma | Ocular retrobulbar haemorrhage |
| Acquired pigmented retinopathy | Exudative retinopathy | Ocular rosacea |
| Acute haemorrhagic conjunctivitis | Eye abscess | Ocular sarcoidosis |
| Acute macular outer retinopathy | Eye allergy | Ocular surface disease |
| Acute myopia | Eye anterior chamber congenital anomaly | Ocular toxicity |
| Acute zonal occult outer retinopathy | Eye burns | Ocular vascular disorder |
| Adenoviral conjunctivitis | Eye colour change | Ocular vasculitis |
| Age-related macular degeneration | Eye complication associated with device | Oculocerebrorenal syndrome |
| AIDS retinopathy | Eye contusion | Oculodentodigital dysplasia |
| Allergic keratitis | Eye degenerative disorder | Oculoglandular syndrome |
| Alstroem syndrome | Eye discharge | Oculogyric crisis |
| Altered visual depth perception | Eye disorder | Oculomucocutaneous syndrome |
| Amaurosis | Eye haemangioma | Oculopharyngeal dystrophy |
| Amaurosis fugax | Eye haematoma | Oculorespiratory syndrome |
| Amblyopia | Eye haemorrhage | Onchocerciasis |
| Amblyopia alcohol | Eye infection | Open angle glaucoma |
| Amblyopia congenital | Eye infection bacterial | Open globe injury |
| Amblyopia strabismic | Eye infection chlamydial | Ophthalmia neonatorum |
| Amblyopia tobacco | Eye infection fungal | Ophthalmia nodosa |
| Angle closure glaucoma | Eye infection gonococcal | Ophthalmic herpes simplex |
| Aniridia | Eye infection helminthic | Ophthalmic herpes zoster |
| Aniseikonia | Eye infection intraocular | Ophthalmic vein thrombosis |
| Anisometropia | Eye infection staphylococcal | Ophthalmoplegia |
| Anomaly of orbit, congenital | Eye infection syphilitic | Ophthalmoplegic migraine |

| SOC Eye Disorders | SOC Eye Disorders | SOC Eye Disorders |
|---|------------------------------|------------------------------------|
| Anophthalmos | Eye infection toxoplasmal | Opitz-G/BBB syndrome |
| Anterior capsule contraction | Eye infection viral | Opsoclonus myoclonus |
| Anterior chamber angle neovascularisation | Eye inflammation | Optic atrophy |
| Anterior chamber cell | Eye injury | Optic disc disorder |
| Anterior chamber cleavage syndrome | Eye irritation | Optic disc drusen |
| Anterior chamber collapse | Eye laser scar | Optic disc haemorrhage |
| Anterior chamber crystallisation | Eye luxation | Optic disc hyperaemia |
| Anterior chamber degeneration | Eye movement disorder | Optic disc pit |
| Anterior chamber disorder | Eye muscle entrapment | Optic disc telangiectasia |
| Anterior chamber fibrin | Eye naevus | Optic disc vascular disorder |
| Anterior chamber flare | Eye oedema | Optic discs blurred |
| Anterior chamber inflammation | Eye opacity | Optic glioma |
| Anterior chamber opacity | Eye pain | Optic ischaemic neuropathy |
| Anterior chamber pigmentation | Eye paraesthesia | Optic nerve compression |
| Anterior segment ischaemia | Eye pruritus | Optic nerve cupping |
| Antimetropia | Eye swelling | Optic nerve disorder |
| Aphakia | Eye symptom | Optic nerve hypoplasia |
| Aphakia congenital | Eye ulcer | Optic nerve infarction |
| Aqueous fibrin | Eyeball avulsion | Optic nerve injury |
| Aqueous humour leakage | Eyelash changes | Optic nerve neoplasm |
| Arcus lipoides | Eyelash discolouration | Optic nerve sheath haemorrhage |
| Argyll-Robertson pupils | Eyelash hyperpigmentation | Optic neuritis |
| Arteriosclerotic retinopathy | Eyelash hypopigmentation | Optic neuritis meningococcal |
| Asthenopia | Eyelash injury | Optic neuropathy |
| Astigmatism | Eyelash thickening | Optic pathway injury |
| Atopic cataract | Eyelid bleeding | Orbit atrophy |
| Atopic keratoconjunctivitis | Eyelid boil | Orbital apex syndrome |
| Atrophy of globe | Eyelid contusion | Orbital compartment syndrome |
| Autoimmune retinopathy | Eyelid cyst | Orbital cyst |
| Autoimmune uveitis | Eyelid degenerative disorder | Orbital granuloma |
| Bacterial blepharitis | Eyelid disorder | Orbital infection |
| Bacterial dacryocystitis | Eyelid erosion | Orbital myositis |
| Bacterial iritis | Eyelid exfoliation | Orbital oedema |
| Balint's syndrome | Eyelid folliculitis | Oscillopsia |
| Basal cell naevus syndrome | Eyelid function disorder | Osteoporosis-pseudoglioma syndrome |
| Basedow's disease | Eyelid haemangioma | Ota's naevus |
| Behcet's syndrome | Eyelid haematoma | Overwear syndrome |

| SOC Eye Disorders | SOC Eye Disorders | SOC Eye Disorders |
|-----------------------------------|---|--------------------------------------|
| Bell's phenomenon | Eyelid infection | Panophthalmitis |
| Benign neoplasm of choroid | Eyelid injury | Papilloedema |
| Benign neoplasm of conjunctiva | Eyelid irritation | Papilloma conjunctival |
| Benign neoplasm of cornea | Eyelid margin crusting | Papillophlebitis |
| Benign neoplasm of eye | Eyelid myoclonus | Paralytic lagophthalmos |
| Benign neoplasm of eyelid | Eyelid naevus | Paraneoplastic retinopathy |
| Benign neoplasm of lacrimal duct | Eyelid oedema | Parinaud syndrome |
| Benign neoplasm of lacrimal gland | Eyelid pain | Parophthalmia |
| Benign neoplasm of optic nerve | Eyelid ptosis | Pars plana cyst |
| Benign neoplasm of orbit | Eyelid ptosis congenital | Pathologic myopia |
| Benign neoplasm of retina | Eyelid rash | Periorbital abscess |
| Bickerstaff's encephalitis | Eyelid retraction | Periorbital cellulitis |
| Binocular eye movement disorder | Eyelid sensory disorder | Periorbital disorder |
| Birdshot chorioretinopathy | Eyelid skin dryness | Periorbital fat atrophy |
| Blau syndrome | Eyelid thickening | Periorbital fat herniation |
| Blebitis | Eyelid tumour | Periorbital haematoma |
| Blepharal papilloma | Eyelid vascular disorder | Periorbital haemorrhage |
| Blepharal pigmentation | Eyelid vellus hair changes | Periorbital infection |
| Blepharitis | Eyelids pruritus | Periorbital inflammation |
| Blepharitis allergic | Faciodigitogenital dysplasia | Periorbital oedema |
| Blepharochalasis | Fat adherence syndrome | Persistent corneal epithelial defect |
| Blepharophimosis | Fibrin deposition on lens postoperative | Persistent pupillary membrane |
| Blepharophimosis congenital | Filariasis | PHACES syndrome |
| Blepharospasm | Flat anterior chamber of eye | Phacolytic glaucoma |
| Blepharosynechia | Floppy eyelid syndrome | Phakomatosis |
| Blindness | Floppy iris syndrome | Photoelectric conjunctivitis |
| Blindness congenital | Foreign body in eye | Photokeratitis |
| Blindness cortical | Foreign body sensation in eyes | Photophobia |
| Blindness day | Foster-Kennedy Syndrome | Photopsia |
| Blindness hysterical | Fraser syndrome | Pigment dispersion syndrome |
| Blindness transient | Fuchs' syndrome | Pigmentary glaucoma |
| Blindness traumatic | Fungal retinitis | Pinguecula |
| Blindness unilateral | Gaze palsy | Pingueculitis |
| Bloch-Sulzberger syndrome | Giant papillary conjunctivitis | Polypoidal choroidal vasculopathy |
| Borderline glaucoma | Glare | Post measles blindness |
| Bowman's membrane disorder | Glassy eyes | Posterior capsule opacification |
| Bowman's membrane injury | Glaucoma | Posterior capsule rupture |
| Brow ptosis | Glaucoma traumatic | Posterior segment of eye anomaly |

| SOC Eye Disorders | SOC Eye Disorders | SOC Eye Disorders |
|---------------------------------------|--|---|
| Candida endophthalmitis | Glaucomatocyclitic crises | Posterior segment of eye anomaly congenital |
| Candida retinitis | Glaucomatous optic disc atrophy | Presbyopia |
| CANVAS syndrome | Graft versus host disease in eye | Presumed ocular histoplasmosis syndrome |
| Capsular block syndrome | Growth of eyelashes | Progressive external ophthalmoplegia |
| Carcinoma in situ of eye | Haemangioma of retina | Prominent epicantal folds |
| Cataract | Halo vision | Prostaglandin analogue periorbitopathy |
| Cataract congenital | Heerfordt's syndrome | Protozoal corneal ulcer |
| Cataract cortical | Hemianopia | Pseudo-blepharoptosis |
| Cataract diabetic | Hemianopia heteronymous | Pseudoendophthalmitis |
| Cataract nuclear | Hemianopia homonymous | Pseudomyopia |
| Cataract operation complication | Hepato-lenticular degeneration | Pseudopapilloedema |
| Cataract subcapsular | Hereditary choroidal dystrophy | Pseudophakic bullous keratopathy |
| Cataract traumatic | Hereditary optic atrophy | Pseudophakic glaucoma |
| Cavernous sinus syndrome | Hereditary retinal dystrophy | Pseudophakodonesis |
| Cellulitis orbital | Hermansky-Pudlak syndrome | Pseudopterygium |
| Chalazion | Herpes ophthalmic | Pseudostrabismus |
| CHARGE syndrome | Herpes simplex necrotising retinopathy | Pseudoxanthoma elasticum |
| Charles Bonnet syndrome | Herpes simplex virus conjunctivitis neonatal | Psychogenic visual disorder |
| Chemical burns of eye | Herpes zoster necrotising retinopathy | Pterygium |
| Chemical eye injury | Heterochromia iridis | Punctate keratitis |
| Chemical iritis | Heteronymous diplopia | Pupil fixed |
| Chiasma syndrome | Heterophoria | Pupillary block |
| Chloropsia | Hippus | Pupillary deformity |
| Cholesterolosis bulbi | Holmes-Adie pupil | Pupillary disorder |
| Chorioretinal atrophy | Homonymous diplopia | Pupillary reflex impaired |
| Chorioretinal degeneration congenital | Hordeolum | Pupillotonia |
| Chorioretinal disorder | Horner's syndrome | Pupils unequal |
| Chorioretinal folds | Hyalosis asteroid | Parutscher retinopathy |
| Chorioretinal scar | Hypermetropia | Quadrantanopia |
| Chorioretinitis | Hypertelorism of orbit | Radiation cataract |
| Choroid melanoma | Hyphaema | Radiation corneal injury |
| Choroid neoplasm | Hypoesthesia eye | Radiation retinopathy |
| Choroid tubercles | Hypopigmentation of eyelid | Raymond-Cestan syndrome |
| Choroidal coloboma | Hypopyon | Recession of chamber angle of eye |

| SOC Eye Disorders | SOC Eye Disorders | SOC Eye Disorders |
|-------------------------------------|-------------------------------------|------------------------------------|
| Choroidal detachment | Hypotelorism of orbit | Refraction disorder |
| Choroidal dystrophy | Hypotony of eye | Refractive amblyopia |
| Choroidal effusion | Idiopathic orbital inflammation | Retinal aneurysm |
| Choroidal haemangioma | IIIrd nerve disorder | Retinal aneurysm rupture |
| Choroidal haematoma | IIIrd nerve injury | Retinal anomaly congenital |
| Choroidal haemorrhage | IIIrd nerve paralysis | Retinal arteriovenous malformation |
| Choroidal infarction | IIIrd nerve paresis | Retinal artery embolism |
| Choroidal neovascularisation | Immune recovery uveitis | Retinal artery occlusion |
| Choroidal rupture | Inclusion conjunctivitis | Retinal artery spasm |
| Choroidal sclerosis | Inclusion conjunctivitis neonatal | Retinal artery stenosis |
| Choroiditis | Infectious crystalline keratopathy | Retinal artery thrombosis |
| Chromatopsia | Infectious iridocyclitis | Retinal collateral vessels |
| Ciliary body degeneration | Infective corneal ulcer | Retinal coloboma |
| Ciliary body disorder | Infective episcleritis | Retinal cyst |
| Ciliary body haemorrhage | Infective iritis | Retinal degeneration |
| Ciliary hyperaemia | Infective keratitis | Retinal depigmentation |
| Ciliary muscle spasm | Infective scleritis | Retinal deposits |
| Ciliary zonular dehiscence | Infective uveitis | Retinal disorder |
| Closed globe injury | Inflammation of lacrimal passage | Retinal drusen |
| Cockayne's syndrome | Injury corneal | Retinal dystrophy |
| Cogan's syndrome | Injury of conjunctiva | Retinal exudates |
| Cohen syndrome | Intra-ocular injection complication | Retinal fibrosis |
| Coloboma | Intraocular haematoma | Retinal haemorrhage |
| Colour blindness | Intraocular melanoma | Retinal infarction |
| Colour blindness acquired | Iridocele | Retinal infiltrates |
| Commotio retinae | Iridocorneal endothelial syndrome | Retinal injury |
| Computer vision syndrome | Iridocyclitis | Retinal ischaemia |
| Congenital astigmatism | Iridodialysis | Retinal melanocytoma |
| Congenital choroidal anomaly | Iridodonesis | Retinal melanoma |
| Congenital corneal anomaly | Iridoplegia | Retinal migraine |
| Congenital epiblepharon | Iridoschisis | Retinal neoplasm |
| Congenital eye disorder | Iris adhesions | Retinal neovascularisation |
| Congenital eye naevus | Iris atrophy | Retinal oedema |
| Congenital eyelid malformation | Iris bombe | Retinal pallor |
| Congenital Horner's syndrome | Iris coloboma | Retinal perivascular sheathing |
| Congenital iris anomaly | Iris convex | Retinal phototoxicity |
| Congenital lacrimal gland anomaly | Iris cyst | Retinal pigment epithelial tear |
| Congenital lacrimal passage anomaly | Iris disorder | Retinal pigment epitheliopathy |

| SOC Eye Disorders | SOC Eye Disorders | SOC Eye Disorders |
|---|--|-----------------------------------|
| Congenital lenticonus | Iris exfoliation | Retinal pigmentation |
| Congenital myopia | Iris haemorrhage | Retinal scar |
| Congenital night blindness | Iris hyperpigmentation | Retinal tear |
| Congenital nystagmus | Iris hypopigmentation | Retinal telangiectasia |
| Congenital oculomotor apraxia | Iris incarceration | Retinal thickening |
| Congenital optic nerve anomaly | Iris injury | Retinal toxicity |
| Congenital retinoblastoma | Iris melanoma | Retinal vascular disorder |
| Congenital scleral disorder | Iris neoplasm | Retinal vascular occlusion |
| Congenital trichomegaly | Iris neovascularisation | Retinal vascular thrombosis |
